#### **5.4.2 Definition of the average daily severity score of mild to severe VMS**

The daily VMS severity score is defined as  $(2xFmo + 3xFse)/(Fmo + Fse)$  for any day before the first dose day, and  $(1xFmi + 2xFmo + 3xFse)/(Fmi + Fmo + Fse)$  for any day on or after the first dose day, where Fmi, Fmo, and Fse are the daily frequencies of mild, moderate, and severe VMS, respectively. It will be rounded off the third decimal place and reported the value to the second decimal place.

The average daily VMS severity of mild to severe VMS at a time point (Baseline, Week 1, 2, 3, 4, ..., 12) is the average of the daily severity of available diary days in the corresponding 7-day window defined in Table 4.

A daily severity score of zero (0) is assigned if it is reported that no VMS occurred on that day. VMS data on the day of Week 12 visit is not used for the calculation of average daily VMS severity. If the count of available VMS data in a specific week is less than four (4), latest diaries in the previous window can be carried as needed to make 4 diaries available in this window. Then the average daily VMS severity in the week is calculated.

#### **5.4.3 Definition of clinical responder**

A clinical responder will be defined as a subject with a cutoff number or greater reduction in the average daily frequency of moderate and severe VMS compared to baseline. The cutoff number of responder criteria will be calculated using anchor-based method, using PGIC as the anchor. The satisfied subjects will be defined as those whose PGIC response is either 6 or 7. The cutoff number is defined as numerical value to maximize the sum of sensitivity and specificity (i.e. maximize the Youden's index) for change from baseline in average daily frequency of moderate to severe VMS. This calculation will use pooled data from all four study arms and both Week 4 and 12 time points.

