6.5.2.5 Patient Global Impression of Change¹⁰

The PGIC is used to assess the subject's rating of overall improvement. Subjects rate their perceived change on a 7-point scale from ‘very much improved’ to ‘very much worse’. See APPENDIX 6 for an example of the PGIC.

If necessary, further details will be provided in a separate study reference manual.

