## 7.9.3 Analysis of Other Efficacy Endpoints

The PGIC score will be analyzed with ANOVA model at Weeks 4 and 12. (Table 14.2.8.1)

The response rate based on PGIC score (i.e. either 6 or 7) will be analyzed with logistic regression at Weeks 4 and 12. (Table 14.2.8.2)

The change from baseline to Weeks 4 and 12 in PSQI total and each domain score will be analyzed with ANCOVA model. The analysis model will include baseline value as a covariate and treatment as fixed effect. (Table 14.2.9.1) In addition, PSQI total score in categories will be summarized for each visit (Table 14.2.9.2). The following categories will be used for the analysis;

- Good sleep quality: PSQI total score  $\leq 5$

- Poor sleep quality: PSQI total score > 5

The ANCOVA model will be applied to analyze the change from baseline to Weeks 4 and 12 in total and each domain score of the MENQOL. The analysis model will include baseline value as a covariate and treatment as fixed effect. (Table 14.2.10)

The change from baseline to Weeks 4 and 12 in each domain i.e. Physical Functioning, Role Physical, Bodily Pain, General Health, Vitality, Social Functioning, Role Emotional, Mental Health, Physical Component Summary [PCS], and Mental Component Summary [MCS]) score of the SF-36 will be analyzed using ANCOVA model with treatment as fixed effects and baseline value as covariate. (Table 14.2.11)

The ANCOVA model will be applied to analyze the change from baseline in the average daily severity score of moderate to severe VMS at Weeks 4 and 12, defined as  $2xFmo + 3xFse$ . The analysis model will include baseline value as a covariate and treatment as fixed effect. (Table 14.2.12)

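### Do PGIC responses 6 and 7 pick out the subjects who got worse, so that the responder cutoff fails?

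*SAP*

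**What the plan says.** The scale is described once, in words, in Protocol 6.5.2.5: "Subjects rate their perceived change on a 7-point scale from ‘very much improved’ to ‘very much worse". No category is given a number there. The reader is referred to the form itself: "See APPENDIX 6 for an example of the PGIC".

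The numbers appear where the scale is used. SAP 5.4.3 has "The satisfied subjects will be defined as those whose PGIC response is either 6 or 7", and Protocol 10.3.6 gives the same definition. SAP 7.9.3 uses the same two codes for a separate analysis: "The response rate based on PGIC score (i.e. either 6 or 7) will be analyzed with logistic regression at Weeks 4 and 12".

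The anchor then fixes the responder cutoff. SAP 5.4.3 sets the direction of the rule, "A clinical responder will be defined as a subject with a cutoff number or greater reduction in the average daily frequency of moderate and severe" symptoms, and the criterion, "The cutoff number is defined as numerical value to maximize the sum of sensitivity and specificity". It also sets the data: "This calculation will use pooled data from all four study arms and both Week 4 and 12 time points". The cutoff serves the first two secondary endpoints in the fixed order, the proportion of responders and the time to response (Protocol 10.3.6; SAP 7.9.1.2 and 7.9.1.3).

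**The concern.** Read in sequence, the protocol starts the scale at its best category and ends at its worst. Counting 1 to 7 along that sentence makes 6 and 7 the two worst answers, yet the analysis rules call those subjects satisfied. The visible text contains no table of codes and labels.

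If the dataset were coded that way, the effect would be serious for these analyses. The cutoff search would look for a VMS reduction that identifies subjects who felt worse and would find none. The responder proportion and time to response could then show no difference between arms, and the sequence would stall before the Insomnia Severity Index. The PGIC response rate in SAP 7.9.3 would count deteriorations as responses.

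**Working it through.** The plan states no cutoff value, so there is no figure to reproduce. The check has three parts: whether the passages conflict, what a reversal would do, and whether it would be seen.

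**1. The passages against the two possible codings**

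| Place | What it fixes | 7 = improved end | 1 = improved end |
|---|---|---|---|
| Protocol 6.5.2.5 | two end labels, no numbers | consistent | consistent |
| Protocol 10.3.6 | 6 or 7 is satisfied | consistent | contradicts |
| SAP 5.4.3 | 6 or 7 is satisfied | consistent | contradicts |
| SAP 7.9.3 | 6 or 7 is response | consistent | contradicts |

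One coding fits all four places; the other contradicts three of them. A sentence that names the ends of a scale from best to worst does not say which end is 1. The conflict arises only if the order of mention is taken to be the numeric code.

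**2. What a reversal would do**

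Let R be the reduction in daily VMS and c the cutoff, with a responder defined by R ≥ c. Then

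J(c) = sensitivity + specificity − 1 = P(R ≥ c | satisfied) − P(R ≥ c | not satisfied).

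If the group labelled satisfied tends to have smaller reductions at every c, J(c) is at most 0 throughout. Its maximum of 0 is then reached only at the edges, where everyone or no one responds.

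The illustration uses these inputs:
- From the protocol: about 364 subjects and two visits, so 364 × 2 = 728 observations.
- Assumed, not in the documents: independent observations; reduction with mean 5 and SD 4; correlation between reduction and PGIC of 0.3, 0.5 or 0.7; category shares from best to worst of 15, 25, 25, 20, 8, 5 and 2%; 100 replicates for each correlation.

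The satisfied share is then 15 + 25 = 40% if 7 is best, and 5 + 2 = 7% if 7 is worst.

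| Correlation | Coding | Mean J | Median cutoff | Median responder rate |
|---|---|---|---|---|
| 0.3 | 7 best | 0.22 | 5.0 | 50% |
| 0.5 | 7 best | 0.36 | 5.4 | 47% |
| 0.7 | 7 best | 0.51 | 5.6 | 45% |
| 0.3 | 7 worst | 0.01 | −6.0 | 100% |
| 0.5 | 7 worst | 0.00 | −8.0 | 100% |
| 0.7 | 7 worst | 0.00 | −8.0 | 100% |

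A negative cutoff is an increase in VMS, at the edge of the simulated data. At correlation 0.3 with 7 worst, the 5th to 95th percentile range of the cutoff is −9.0 to 12.8, so the search sometimes lands on the opposite edge, where no one responds. The algebra and the simulation agree on the conditional statement. Both take the reversal as given, so neither is evidence that it exists.

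**3. Would it be seen?**

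SAP 7.9.1.2 requires the ROC curve and the cutoff as outputs. With a reversed anchor, the curve for the rule R ≥ c would lie on or below the diagonal and the cutoff would sit at the edge of the data. Because the cutoff is computed on pooled arms, its direction can be checked without treatment codes. SAP 7.1 provides a blinded data review before database lock at which data handling rules can be added.

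**The case for a change.** The best case for acting is that, wherever the plan gives a scoring direction for its other symptom measures, high is bad: PSQI (Protocol 6.5.2.3), ISI (SAP 7.9.1.4), MENQOL (SAP 5.4.15) and the VMS severity weights (SAP 5.4.2). A programmer might carry that habit over to PGIC. The cutoff is estimated from the trial's own data and feeds endpoints in the fixed sequence, and the final analysis is run unblinded after database lock (SAP 3.3). A correction made then could look post hoc, whereas naming the categories costs a sentence.

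Part of this stands. No visible text maps each number to a label, and labels would be tidier. The rest is weaker. The direction of symptom-burden scales says nothing about the coding of a rating of change, and the plan itself says that 6 and 7 on this scale are favourable. A programmer does not have to guess, because the form shows the categories. Which end carries which number is a fact about the questionnaire and not an analyst's choice, so reading it off correctly is not a data-driven decision whenever it is done.

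**Conclusion.** The concern does not hold as an error in the plan. The quoted passages contradict each other only under an added assumption, that the order in which the end labels are mentioned is the numeric code. Without it they are compatible, and every use of the numbers implies that 7 is the improved end. The codes would be on the Appendix 6 form, which was not part of the text reviewed and so cannot be called missing.

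The conditional harm is real: a Youden index of about 0 in place of 0.22 to 0.51 under the assumptions above, and a reversed PGIC response rate. Nothing in the documents shows that the condition is met. It would affect two secondary endpoints, which are reached only after the co-primary endpoints succeed, one other endpoint, and through the sequence the ISI test. The co-primary analyses are untouched. This is a gap in detail that analysts with the instrument in hand will fill correctly, and the planned ROC output and blinded data review make an unnoticed reversal unlikely. The conclusion rests on the form agreeing with the three analysis rules. If it did not, the mismatch would be plain as soon as the form was compared with the rules.

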#### **5.4.4 Definition(s) of baseline(s)**

Unless otherwise specified, the baseline values are the last available assessment before the first dose of randomized treatment.

#### **5.4.5 Definition(s) of (percent) change from baseline(s)**

For numerical variables, change from baseline will be calculated as the post-baseline value minus the baseline value. If percent change from baseline is required, then percent change from baseline will be calculated as the change from baseline divided by the baseline value, multiplied by 100. If baseline value cannot be determined for a particular variable, the change from baseline and percent change from baseline will not be calculated.

#### **5.4.6 Derived visits**

The derived analysis visit windows are outlined in Table below.

**Table 5 Derived Analysis Visit Windows**

	Nominal day	Window
Baseline	NA	NA
Day 1	Day 1 (First dose day)	NA
Week 2	Day 15	Day 7 to 21
Week 4	29	Day 22 to 42
Week 8	57	Day 43 to 70
Week 12	85	Day 71 to 98
Week 16 (FU)	115	NA

The analysis visits are derived according to the following criteria:

- The unscheduled visits are not used for the deriving.
- If a study visit is the only one in an analysis window, this study visit becomes the derived analysis visit.
- If there are multiple visits in a visit window, the closest visit to the nominal day becomes the analysis visit. In the event that two visits are the closest visits to the nominal day and equally distanced to the nominal day, the visit after the nominal day becomes the derived visit.
- The follow-up visit will not be derived. The study visit will be used.
- Unscheduled visits and retests (same visit number assigned), will not be displayed in by-visit summary tables, but will be included in the data listings. All data will be listed. Listings will include treatment, scheduled, unscheduled, retest and early discontinuation data.
- The screening and run-in visits are carried to derived visits
- The efficacy endpoints based on diary data use different windows. See Section 5.4.1.

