5.2.3 Double-blind Treatment (Visits 3 through 7)

Subjects who successfully complete Screening and Placebo Run-in periods will return to the clinic for the Randomization visit on Day 1 and participate in the Double-blind Treatment period.

Inclusion and exclusion criteria will be reviewed to confirm eligibility prior to randomization.

Randomized subjects who are withdrawn early from the study should, where possible, complete the procedures scheduled for the EOT (Week 12) visit as soon as possible after withdrawal. Every effort should be made to maintain randomized subjects on study, even in cases where treatment has been discontinued.

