2. Physical examination:
  - a. Complete: abdominal, cardiovascular, general appearance, head, eyes, ears/nose/throat, lymph nodes, musculoskeletal, neck, neurological, dermatological, respiratory, and other.
  - b. Routine: abdominal, cardiovascular, general appearance, respiratory, and other.
3. Vital signs (including sitting blood pressure, pulse rate, and tympanic body temperature) will be measured at all visits.
4. Transvaginal ultrasound and endometrial biopsy to be performed only on subjects who have a uterus.
5. VMS diary data will be collected for 14-days duration during Screening and for 14-days duration during the Placebo Run-in period for eligibility determination.
6. Investigator should instruct subject to administer dose at least 2 hours after starting the evening meal and approximately 30 minutes before bedtime.
7. Blood samples for MT-8554 PK will be collected at Visits 3 through 7. Date and time of most recent dose will be recorded at Visits 4 through 7.
8. The EOT should be performed for subjects who complete as well as those who withdraw from the study early.
9. The Follow-up visit will be conducted by phone 30 days after the EOT visit for subjects who complete as well as those who withdraw early from the study. The Follow-up visit should not be done for subjects enrolling in the long-term extension study, should it be implemented.
10. Baseline assessments for transvaginal ultrasound and endometrial biopsy at baseline may be scheduled and conducted at any time during the Screening period or the Placebo Run-in period, but at least 7 days prior to randomization, to accommodate site specific scheduling. Note: subjects qualifying based on transvaginal ultrasound will proceed to endometrial biopsy.
11. Site staff will make periodic calls to the subjects at a minimum during weeks where no in clinic visits occur, to confirm compliance with daily VMS diary data entry [REDACTED]

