### 7.10.2 Laboratory Tests

For all continuous laboratory parameters, the lab values and change from baseline to post baseline visits are summarized by treatment group and visit.

For all discrete laboratory parameters, the lab values are summarized with count and percentage by treatment group and visit. (Table 14.3.2.1, Table 14.3.2.2, Table 14.3.2.3, Table 14.3.2.4, Table 14.3.2.5)

The lab tables will be generated for each Lab categories (Hematology, Coagulation, Biochemistry and Hormones and Urinalysis).

All laboratory data will be listed with clinically relevant values flagged (L=Lower than lower limit of normal range or H=Higher than upper limit of normal range).

In addition, following clinical relevant ranges (and flags) will also be considered for summary table. The count and percent of subjects meeting the criteria will be presented. (Table 14.3.2.6)

- ALT  $\geq 3 \times$  Upper Limit of Normal Range (ULN), 5 $\times$  ULN, 8 $\times$  ULN, 10 $\times$  ULN
- AST and/or ALT  $\geq 3 \times$  ULN, 5 $\times$  ULN, 8 $\times$  ULN, 10 $\times$  ULN
- AST and/or ALT  $\geq 3 \times$  ULN with Total bilirubin  $\geq 2 \times$  ULN
- Total bilirubin  $\geq 2 \times$  ULN
- Creatinine  $\geq 2 \times$  ULN

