### 7.10.8 Other Safety Assessments

Total score of PHQ-8 and total score of GAD7 will be summarized descriptively in tables by treatment and scheduled visit. (Table 14.3.8, Table 14.3.9) The data listings will be generated.

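### An early-termination visit that follows an on-time or late scheduled visit in the same window, or that falls on Days 2–6, is left out of the window-based by-visit safety summaries

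*SAP*

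**What the plan says.** SAP 5.4.6 and Table 5 assign visits to windows: Week 2 is Days 7–21 (nominal Day 15), Week 4 is Days 22–42 (nominal Day 29), Week 8 is Days 43–70 (nominal Day 57) and Week 12 is Days 71–98 (nominal Day 85). Day 1 is the first dose day only. Where two visits share a window, "If there are multiple visits in a visit window, the closest visit to the nominal day becomes the analysis visit". If they are equally distant, "the visit after the nominal day becomes the derived visit".

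The early-termination visit is a protocol visit, not an unscheduled one. SAP Table 1 notes that "The EOT should be performed for subjects who complete as well as those who withdraw from the study early". Protocol 5.2.3 asks women who withdraw to "complete the procedures scheduled for the EOT (Week 12) visit as soon as possible after withdrawal", so the visit can fall on any study day.

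Table 5 has no end-of-treatment or early-termination row. The one place where 5.4.6 mentions these data is the listings: "Listings will include treatment, scheduled, unscheduled, retest and early discontinuation data".

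The by-visit tables at issue include laboratory tests (SAP 7.10.2), where "the lab values and change from baseline to post baseline visits are summarized by treatment group and visit", and the two mood scales (SAP 7.10.8): "Total score of PHQ-8 and total score of GAD7 will be summarized descriptively in tables by treatment and scheduled visit". By contrast, SAP 7.10.4 ends its QTcB and QTcF shift tables at the end-of-treatment or early discontinuation visit.

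**The concern.** The assessment made when a woman leaves the study can be the most informative safety measurement she contributes. The closest-to-nominal rule prefers the measurement nearest the calendar target. After an on-time or late scheduled visit, that is always the earlier one, taken before she withdrew.

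For example, a woman attends Week 4 on Day 29 and has her early-termination visit on Day 36. Both fall in the Week 4 window. Day 29 is 0 days from nominal and Day 36 is 7 days away, so the Week 4 row uses Day 29 and the Day 36 values appear in no row. A woman whose termination visit is on Day 5 has no window at all.

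If harm drives withdrawal, tables built this way could understate it in the arm where more women leave. The exposure is greatest for PHQ-8 and GAD7. The visible SAP text gives them no threshold count, shift table or endpoint summary, and the protocol sections on these scales (6.8.1 and 6.8.2) state no rule for reporting abnormal scores as adverse events.

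**Working it through.** The plan states no figure for this, so the check applies Table 5 to each possible early-termination day.

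**Inputs.** Windows, nominal days and tie rule: SAP Table 5. Scheduled visits on Days 15, 29 and 57, each ±3 days: protocol Table 1. Early-termination day: each of Days 2 to 84, which is 83 days. Scheduled visits that fall before the termination day are taken as attended.

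**Days with no window.** Days 2–6: 5 days.

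**Days lost to a competing visit, scheduled visits exactly on nominal days.** Any later day in the same window is farther from nominal, so it is dropped:
- Week 2 window: Days 16–21, 6 days
- Week 4 window: Days 30–42, 13 days
- Week 8 window: Days 58–70, 13 days
- Total: 6 + 13 + 13 = 32

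With the gap, 32 + 5 = 37 days, and 37/83 = 44.6%. Days 71–84 are never lost, because no earlier scheduled visit falls in the Week 12 window.

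**Scheduled visits off nominal.** If a scheduled visit is *d* days from nominal, each window loses *d* fewer days.
- Visit *d* days late: any later termination visit in that window is farther from nominal and is dropped.
- Visit *d* days early: a termination visit up to 2*d* days later is as close or closer, and a tie goes to the visit after nominal. The termination visit is then kept and the scheduled visit is dropped. With Week 4 on Day 26 (*d* = 3), termination visits on Days 27–32 are kept.

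With all three visits shifted equally, the number of lost days is 37 − 3*d*:

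| *d* | Days lost | Share of 83 |
|---|---|---|
| 0 | 37 | 44.6% |
| 1 | 34 | 41.0% |
| 2 | 31 | 37.3% |
| 3 | 28 | 33.7% |

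If each visit varies independently over −3 to +3 with equal weight, the mean of *d* is (3+2+1+0+1+2+3)/7 = 12/7. The expected loss is 37 − 3 × 12/7 = 31.86 days, and 31.86/83 = 38.4%.

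**Which assessments are affected.** The wording selects a visit, but the SAP does not say outright whether selection is by whole visit or by assessment.
- PHQ-8, GAD7, vital signs and routine laboratory tests are measured at every treatment visit. The scheduled value displaces the termination value under either reading.
- Hormones, ECG, weight and breast examination are measured at Visit 7 but not at Weeks 2, 4 or 8. Under whole-visit selection, the literal reading, they go with the dropped visit although the retained visit has no such record. Under per-assessment selection they have no competitor and are lost only on Days 2–6.
- Ultrasound and biopsy are also post-baseline only at Visit 7. A termination visit kept before Day 71 is labelled Week 2, 4 or 8, whereas the biopsy shift table in SAP 7.10.7.2 runs to Week 12. The window rule would leave that biopsy out of the shift.

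**The case against.** The strongest reply is that the SAP does not erase these data.

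- The two QTc shift tables name the early discontinuation visit as their endpoint.
- Clinically significant vital-sign, ECG and laboratory abnormalities are to be reported as adverse events (protocol 6.7.3, 6.7.4 and 6.7.7). The adverse-event tables, including events leading to discontinuation, do not use visit windows.
- Women who stop drug are encouraged to stay in the study (protocol 4.5.1), so the termination visit concerns study withdrawal and may come well after the last dose.
- For a row labelled Week 4, a Day 29 value is the natural one.
- Vital signs, ECG and the mood scales are tabulated by scheduled visit. That phrase might mean the collected visit label, not the Table 5 window.
- The list of tables in SAP Section 11 is not in the public text, so an end-of-treatment row there cannot be ruled out. SAP 7.1 also allows further data-handling rules before database lock.

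Most of this stands, and it limits the point. A reader might infer that withdrawal values disappear from every safety table; the QTc shift and adverse-event tables show otherwise. A reader might infer that any termination visit soon after a scheduled one is lost; an early scheduled visit can let the termination visit win. A reader might multiply the day share by the 364 planned subjects, or conclude that the active arms look safer than they are. The documents give no withdrawal rate, timing or split by arm, so they support neither step.

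The reply does not remove the rule itself. Section 5.4.6 exempts only diary endpoints from these windows and makes no provision for a termination visit that loses its window or has none. If scheduled visit did mean the collected label, early-termination values would sit under Visit 7, which is Week 12, and that too would need stating.

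**Conclusion.** The point holds as a minor one that is cheap to fix. As written, 5.4.6 leaves an early-termination visit out of the window-based by-visit summaries when it follows an on-time or late scheduled visit in the same window, or falls on Days 2–6. This covers 45% of the calendar days from Day 2 to Day 84 with visits on nominal days, and about 38% averaged over the ±3-day allowance. Those shares assume that earlier scheduled visits were attended; the 38% also assumes equal weight on each permitted visit day.

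For PHQ-8, GAD7, vital signs and routine laboratory tests the displacement does not depend on how the rule is read. For hormones, ECG, weight and breast examination it depends on whole-visit selection, apart from Days 2–6. PHQ-8 and GAD7 have the least cover elsewhere. Understatement of harm is possible if harm drives withdrawal, but its direction and size are not established.

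**What to change.** Make two changes to the SAP:

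1. In 5.4.6, apply the closest-to-nominal rule separately to each assessment, using non-missing values only. A visit that did not make an assessment then cannot displace one that did.
2. Add a row, End of treatment (Visit 7: Week 12 or early termination), to the by-visit tables for PHQ-8, GAD7, vital signs, weight, laboratory tests, hormones, ECG, breast examination and the endometrial assessments. Take Visit 7 whatever its study day. This row is what recovers PHQ-8, GAD7, vital signs and routine laboratory values, and it brings 5.4.6 into line with 7.10.4.

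Leave the Week 2 window as it is. Opening it on Day 2 would label a Day 2 value as Week 2, and the new row already captures those visits.

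The cost is SAP wording and one row per table, with no new data. The drawback is that the row mixes different treatment durations, so it should be labelled accordingly and read beside the by-visit rows.
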